10.3 Nivolumab

Nivolumab Injection is a clear to opalescent, colorless to pale yellow liquid, which may contain light (few) particulates. The drug product is a sterile, non-pyrogenic, single-use, isotonic aqueous solution formulated at 10 mg/mL in sodium citrate, sodium chloride, mannitol, diethylenetriaminepentacetic acid (pentetic acid), and polysorbate 80 (Tween™ 80), at pH 6.0 and includes an overfill to account for vial, needle, and syringe holdup. It is supplied in 10-cc Type I flint glass vials, stoppered and sealed with aluminum seals. Vials must be stored at 2°C to 8°C (36°F to 46°F) and protected from light and freezing.

Nivolumab injection is to be administered as an IV infusion through a 0.2-micron to 1.2-micron pore size, low-protein binding (polyethersulfone membrane) in-line filter at the protocol-specified doses for 30 minutes. It is not to be administered as an IV push or bolus injection.

At the fixed dose of 240 mg or 480 mg, Nivolumab injection can be infused undiluted or diluted so as not to exceed a total infusion volume of 120 mL.

Care must be taken to assure sterility of the prepared solution as the product does not contain any antimicrobial preservative or bacteriostatic agent. Nivolumab infusions are compatible with polyvinyl chloride (PVC) or polyolefin containers and infusion sets, and glass bottles. During drug product preparation and handling, vigorous mixing or shaking is to be avoided. The administration of Nivolumab infusion must be completed within 24 hours of preparation.

Please refer to the current IB for preparation, storage and handling details regarding Nivolumab. Nivolumab will be supplied at no charge to patients on this study by BMS.

At the end of the study period, Bristol-Myers Squibb Company will not continue to supply study drug to subjects/investigators unless the sponsor-investigator chooses to extend their study. The investigator is responsible to ensure that the subject receives appropriate standard of care or other appropriate treatment in the independent medical judgement of the Investigator to treat the condition under study.

11. ADVERSE EVENTS

The descriptions and grading scales found in the NCI CTCAE v4 will be utilized for AE assessment. A copy of the CTCAE v4 can be downloaded from the CTEP website at <http://ctep.cancer.gov>. All forms for AE/SAE recording and reporting can be found in the Study Procedure Manual or in the EDC system (Documents and Information Tab).

11.1 Definitions

11.1.1 Adverse Event (AE)

An adverse experience is defined as any unintended or abnormal clinical observation that is not of benefit to the patient whether or not considered related to the study vaccine. Either the condition was not present prior to signature of informed consent, or it has worsened in intensity or frequency following exposure to the study therapy. The following are examples of AEs:

- Unintended or unfavorable sign or symptom
- A disease temporally associated with participation in the protocol

- An intercurrent illness or injury that impairs the well-being of the subject

Hospitalization for elective surgery or routine clinical procedures that are not the result of an AE (e.g., surgical insertion of central line) should not be recorded as an AE.

Disease progression should not be recorded as an AE, unless it is attributable to the study regimen by the site investigator.

11.1.2 Serious Adverse Event (SAE)

A **Serious Adverse Event (SAE)** is any untoward medical occurrence that at any dose:

- results in death
- is life-threatening (defined as an event in which the participant was at risk of death at the time of the event; it does not refer to an event which hypothetically might have caused death if it were more severe)
- requires inpatient hospitalization or causes prolongation of existing hospitalization (see **NOTE** below)
- results in persistent or significant disability/incapacity
- is a congenital anomaly/birth defect
- is an important medical event (defined as a medical event(s) that may not be immediately life-threatening or result in death or hospitalization but, based upon appropriate medical and scientific judgment, may jeopardize the subject or may require intervention [e.g., medical, surgical] to prevent one of the other serious outcomes listed in the definition above.) Examples of such events include, but are not limited to, intensive treatment in an emergency room or at home for allergic bronchospasm; blood dyscrasias or convulsions that do not result in hospitalization.)
- Suspected transmission of an infectious agent (e.g., pathogenic or nonpathogenic) via the study drug is an SAE.

Although pregnancy, overdose, potential drug-induced liver injury (DILI), and cancer are not always serious by regulatory definition, these events must be handled as SAEs. Potential drug induced liver injury is defined as:

- 1) AT (ALT or AST) elevation > 3 times upper limit of normal (ULN)
AND
- 2) Total bilirubin > 2 times ULN, without initial findings of cholestasis (elevated serum alkaline phosphatase)
AND
- 3) No other immediately apparent possible causes of AT elevation and hyperbilirubinemia, including, but not limited to, viral hepatitis, pre-existing chronic or acute liver disease, or the administration of other drug(s) known to be hepatotoxic.

11.1.3 Unexpected Adverse Event

For this study, an AE is considered unexpected when it varies in nature, intensity or frequency from information provided in the current IB, prescribing information or when it is not included in the informed consent document as a potential risk. Unexpected also refers to AEs that are mentioned in the IB as occurring with a class of drugs or are anticipated from the

pharmacological properties of the drug, but are not specifically mentioned as occurring with the particular drug under investigation.

11.1.4 Relatedness

AEs will be categorized according to the likelihood that they are related to the study drug(s). Specifically, they will be categorized using the following terms:

Unrelated	Adverse Event is not related to the study drug(s)
Unlikely	Adverse Event is doubtfully related to the study drug(s)
Possible	Adverse Event may be related to the study drug(s)
Probable	Adverse Event is likely related to the study drug(s)
Definite	Adverse Event is clearly related to the study drug(s)

11.1.5 Cardiac events management

Based on the total clinical experience with poxvirus vectors for anticancer vaccines, including CV301's predecessor product PANVAC, a causal relationship of cardio-toxicity following treatment with CV301 and/or PANVAC is unlikely. Nonetheless, a proactive approach in pharmacovigilance will be applied prospectively, requesting from the investigators a deeper characterization of every case with a cardiac AE with the working hypothesis that myocarditis/pericarditis may be the underlying cause. As deemed necessary by the investigator, ECG and/or troponin testing may be performed in the presence of any cardiac symptoms, in order to exclude the diagnosis of myo-/pericarditis. The reporting of cardiac events follows the standard processes as outlined above.

11.2 Reporting

11.2.1 Adverse Events

- AEs will be recorded from time of signed informed consent until 100 days after discontinuation of study drug(s) or until a new anti-cancer treatment starts, whichever occurs first.
- AEs will be recorded regardless of whether or not they are considered related to the study drug(s).
- All AEs will be recorded in the subject's medical record and on the appropriate study specific eCRF form within the EDC system.
- AEs considered related to study drug(s) will be followed until resolution to \leq Grade 1 or baseline, deemed clinically insignificant, and/or until a new anti-cancer treatment starts, whichever occurs first.

11.2.2 Serious Adverse Events (SAEs)

11.2.2.1 Site Requirements for Reporting SAEs to HCRN

- SAEs will be reported from time of signed informed consent until 100 days after discontinuation of study drug(s) or until a new anti-cancer treatment starts, whichever occurs first.

- SAEs will be reported on the SAE Submission Form **within 1 business day** of discovery of the event.
- SAEs include events related and unrelated to the study drug(s).
- All SAEs will be recorded in the subject's medical record and on the appropriate study specific eCRF form within The EDC system.
- All SAEs regardless of relation to study drug will be followed until resolution to \leq Grade 1 or baseline and/or deemed clinically insignificant and/or until a new anti-cancer treatment starts, whichever occurs first.

The site will submit the completed SAE Submission Form to HCRN **within 1 business day** of discovery of the event. The form may be submitted to HCRN electronically to [contact]. The site investigator is responsible for informing the IRB and/or other local regulatory bodies as per local requirements.

The original copy of the SAE Submission Form and the email correspondence must be kept within the study file at the study site.

Once the SAE has resolved (see resolution guidelines listed in 11.2.2.1), sites must submit a follow-up SAE Submission Form within a reasonable timeframe to HCRN electronically to [contact].

11.2.2.2 HCRN Requirements for Reporting SAEs to Bavarian Nordic and Bristol Myers Squibb (BMS)

HCRN will report all SAEs to Bavarian Nordic (BN) at [contact] and BMS at [contact] **within 1 business day** of receipt of the SAE Submission Form from a site. Follow-up information will be provided to Bavarian Nordic and BMS **within 1 business day** as it is received from site.

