5.1.4 Adjuvant Therapy

Once patients in the post-operative period are deemed ready to begin therapy (about 6-8 weeks after surgery) or for those subjects that are deemed unresectable and continue with treatment:

- Patients in the control arm (Arm A) will receive 8 cycles of mFOLFOX6 in addition to nivolumab given every 2 weeks through completion of chemotherapy: Cycle 5 – Cycle 12. The treatment order for Arm A is Nivolumab followed by mFOLFOX6.
- Patients in the experimental arm (Arm B) will receive 8 cycles of mFOLFOX6 in addition to nivolumab and FPV-CV301 boosters given every 2 weeks through completion of chemotherapy: Cycle 5 - Cycle 12. For Arm B the order of administration is Nivolumab followed by the vaccination at least one hour prior to mFOLFOX6.

If possible, nivolumab (Arm A and Arm B) +/- the CV301 (Arm B) will be administered on the day (+2 days) that systemic chemotherapy resumes. We will re-collect peripheral blood for evaluation of correlates per the study calendar. For Arm B the order of administration is Nivolumab followed by the vaccination at least one hour prior to mFOLFOX6. A window of +2 days between administration of Nivolumab +/- vaccination and mFOLFOX6 will be allowed. This window will accommodate subjects that receive their chemotherapy locally. If there is more than a 2-day delay for any reason, administration of study drugs should be re-aligned so that the chemotherapy falls within +2 days with the next cycle.

In the event that patients in the experimental arm suffer complications that render them unfit for adjuvant systemic chemotherapy or that they cannot complete their adjuvant systemic chemotherapy due to toxicity, patients will still be eligible to receive their scheduled nivolumab and/or CV301 provided the investigators deem them fit enough to do so.

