5.6 Reproductive Information

There is no information about how an immune response against CEA and MUC-1 might affect sperm function, egg function, or growth of an unborn baby. It is not recommended to become pregnant, breast feed, father children or donate sperm from the time of informed consent until 4 months after the last dose of vaccine. For those subjects, that do not receive the vaccine this is not applicable and information below provides timeframe for birth control.

Nonclinical findings suggest for Nivolumab a potential risk to human pregnancy. Hence, Nivolumab dosing during pregnancy is prohibited. In addition, women of childbearing potential (WOCBP) receiving Nivolumab will be instructed to adhere to contraception from the time of informed consent, during treatment and for 5 months after the last dose of Nivolumab. This timeframe is also applicable to breastfeeding. Men receiving Nivolumab are not required to use contraception but consideration should be given for the timeframe outlined per package insert for chemotherapy. This also applies to donation of sperm.

The two contraception methods can be comprised of two barrier methods, or a barrier method plus a hormonal method.

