6. TOXICITIES AND DOSE DELAYS/DOSE MODIFICATIONS

Guidelines for dose delays and dose modifications are described below, and applicable to the start of each cycle as well as during the cycle if treatment-related toxicities occur. Subjects enrolled in this study will be evaluated clinically and with standard laboratory tests before and at regular intervals during their participation in this study as specified in Study Calendar & Evaluations. The NCI Common Terminology Criteria for Adverse Events (CTCAE) v4 will be used to grade adverse events. Subjects will be evaluated for adverse events (all grades), serious adverse events, and adverse events requiring study drug interruption or discontinuation as specified in Study Calendar & Evaluations.

Dose modifications are always based on the dose used in the previous cycle.

The investigator may attribute each toxicity event to the vaccine, nivolumab, mFOLFOX6, or any component of the combination therapy. Reduction or holding of one agent and not the other agent is appropriate if, in the opinion of the investigator, the toxicity is related to one of the study drugs. For example, if mFOLFOX6 is held due to an AE attributed to that component or the combination, then the vaccine and/or Nivolumab may continue to be administered. The drug to which the investigator is attributing the AE must be documented. If there is more than a 2-day delay for any reason, administration of study drugs should be re-aligned so that the chemotherapy falls within +2 days with the next cycle.

6.1 mFOLFOX6

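### SAE reporting closes at 100 days, so Section 11 states no duty to report a pregnancy conceived late in the 5-month contraception period after nivolumab

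*Combined protocol and SAP*

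**What the plan says.** Section 11.1.2 names pregnancy, with overdose, potential drug-induced liver injury and cancer, as not always serious in the regulatory sense, and adds that "these events must be handled as SAEs".

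Section 11.2.2.1 sets the reporting window: "SAEs will be reported from time of signed informed consent until 100 days after discontinuation of study drug(s"), or to the start of new cancer treatment if that is sooner. A reported SAE is followed to Grade 1 or baseline, "and/or deemed clinically insignificant and/or until a new anti-cancer treatment starts, whichever occurs first". Neither rule treats pregnancy separately. Ordinary adverse events share the same limit in Section 11.2.1: "AEs will be recorded from time of signed informed consent until 100 days after discontinuation of study drug(s").

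Section 5.6 sets two longer periods. Women of childbearing potential on nivolumab use contraception from consent, "during treatment and for 5 months after the last dose of Nivolumab", because nonclinical findings suggest a risk to pregnancy. For CV301, it advises against pregnancy, breastfeeding, fathering children and sperm donation "from the time of informed consent until 4 months after the last dose of vaccine".

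Under Section 5.1.5, nivolumab is planned up to Cycle 36 in both arms. Arm B also receives eight maintenance vaccine doses at 12-week intervals.

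**The concern.** The protocol identifies a hazard to pregnancy, tells women how long to avoid conceiving because of it, and classes pregnancy as an event to be handled like an SAE. The reporting rule then stops before that period ends. A site that follows Section 11.2.2.1 as written need not report a woman who conceives four months after her last nivolumab dose. Onward notice to the two drug suppliers starts from the site's SAE form (Section 11.2.2.2), so they need not hear of it either. Exposed pregnancies in this trial will be rare, which makes each one worth capturing.

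The new-treatment clause adds to the problem. It can close the window before day 100. It can also end follow-up of a pregnancy already reported, and the other stopping points for SAE follow-up do not call for a birth outcome.

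**Working it through.** The protocol states no figure for this gap, so there is none to reproduce. The check is calendar arithmetic.

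**Inputs**
- SAE window: 100 days after discontinuation of study drug(s) (11.2.2.1).
- Nivolumab period: 5 months after the last dose (5.6). Five calendar months are 150 to 153 days, depending on the start date.
- CV301 period: 4 months after the last vaccine (5.6), which is 120 to 123 days.
- Maintenance cycle: 28 days (Section 7).

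**Base case.** Nivolumab is the last study drug, discontinuation is dated at its last dose, and the date of conception governs.
- Gap = (150 to 153) − 100 = 50 to 53 days.
- As a share of the period: 50/150 = 33%; 53/153 = 35%.

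**If the 100 days start later.** Let L be the days from the last nivolumab dose to the date on which the 100 days begin. Gap = max(0, (50 to 53) − L).

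| L (days) | Gap (days) |
|---|---|
| 0 | 50-53 |
| 14 | 36-39 |
| 28 | 22-25 |
| 53 or more | 0 |

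Two things can make L positive. First, discontinuation is not defined; dating it at the end of the last 28-day cycle gives L = 28. Second, another study drug may outlast nivolumab. Section 6 says "Reduction or holding of one agent and not the other agent is appropriate if, in the opinion of the investigator", the toxicity is attributed to one drug. Section 5.1.4 says that Arm B patients who are unfit for chemotherapy, or cannot complete it, may go on: "patients will still be eligible to receive their scheduled nivolumab and/or CV301 provided the investigators deem them fit enough to do so".

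**If new cancer treatment starts on day t, before day 100.** Gap = (150 to 153) − t. For illustration, t = 60 gives 90 to 93 days.

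**CV301.** Let d be the days from the last vaccine to the last study drug. Gap = max(0, (120 to 123) − 100 − d) = max(0, (20 to 23) − d).
- The first maintenance vaccine cycle is not stated. If it is Cycle 13, the eighth dose falls at Cycle 13 + 3 × 7 = 34. With nivolumab to Cycle 36, d = 2 × 28 = 56 and there is no gap.
- If vaccine and the last study drug stop together, d = 0 and the gap is 20 to 23 days.

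**Does anything else in the protocol close the gap?**
- AE recording ends at the same 100 days (11.2.1), and the last dedicated safety contact is at day 100 (footnote 12).
- The calendar lists AE review in follow-up, every 3 months under footnote 13. That footnote says departures from its schedule are not deviations, and it does not extend the window in 11.2.2.1.
- Inclusion criterion 9 tells a woman who becomes pregnant to inform her physician. No onward reporting step is attached.

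**Timing of a follow-up question.** Count contacts from the last nivolumab dose. A month-6 contact falls one calendar month (28 to 31 days) after the 5-month period ends. With the calendar's 14-day window it could come only 14 to 17 days after, too early to rely on for a late conception. A month-9 contact falls four months (120 to 123 days) after, or 106 to 109 days at its earliest.

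**The case against.** The best reply is that nothing in the protocol says the reporting window must equal the contraception period. The 5 months is an instruction to participants, and the 100-day limit is used consistently for AEs, SAEs and the last safety visit, which suggests a deliberate single window. That stands as far as it goes: this is a design choice that can be improved, not an arithmetical error. It does not explain why an event singled out for SAE handling stops being reportable while the stated precaution still runs.

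A reader might infer that a pregnancy after day 100 carries no reporting duty at all. The documents do not support that. Section 11 places the AE and SAE forms in a Study Procedure Manual and the EDC system. Neither was available, nor were the consent pages, and any of them may contain pregnancy instructions. What can be said is that Section 11 states no such duty.

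A reader might also take 50-53 days as settled. It depends on dating discontinuation at the last nivolumab dose and on conception, not recognition, deciding whether the event falls in the window. The protocol fixes neither. A pregnancy conceived by day 100 and found later is arguably still reportable.

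The objection that few patients are affected is also fair. At most 78 are enrolled, the number of women of childbearing potential is not given, and a missed report requires conception despite advice on contraception.

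**Conclusion.** The point holds as a modest gap in safety reporting. Sections 11.1.2, 11.2.2.1 and 5.6 do not fit together. On the planned course in either arm, with discontinuation dated at the last nivolumab dose, Section 11 states no duty to report a conception in the last 50-53 days of the 5-month period, about a third of it. Dating discontinuation 28 days later gives 22-25 days, and a study drug that continues 53 days or more beyond nivolumab removes the nivolumab gap. New cancer treatment before day 100 lengthens it. For the vaccine there is no gap on a Cycle 13 to 34 schedule with nivolumab to Cycle 36, and at most 20-23 days otherwise.

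The number affected is probably small. Sample size, alpha and the survival analysis are untouched, and no efficacy conclusion changes. The case for acting is that the protocol already names the risk and the correction is cheap.

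The pregnancy-test wording is a separate, minor matter. Criterion 9 requires a negative serum test. Footnote 5 and the calendar row accept urine or serum, and footnote 5 makes the pre-dose test conditional on clinical judgement. Its timing rule before each CV301 dose gives a minimum of 2 days and no maximum. A reader might infer that testing is unbounded, but the same sentence requires a test in each month of nivolumab and the calendar places tests throughout treatment.

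**What to change.** Keep the 100-day window and add to Section 11.2.2.1, in substance: *Any pregnancy in a participant conceived up to 5 months after the last nivolumab dose or 4 months after the last CV301 dose, whichever is later, is reported when recognised, whether or not further cancer therapy has begun, and is followed to its outcome. A partner's pregnancy conceived up to 4 months after a male participant's last CV301 dose is handled in the same way, with the partner's consent.* The partner sentence is needed because Section 5.6 also advises against fathering children in that period.

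Ask about pregnancy at the existing 3-monthly follow-up contacts through about month 9. The added text must carry the duty, because those contacts are not binding.

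As a separate minor edit, align footnote 5 and the calendar row with criterion 9: a mandatory test before the first dose, with one sample type. Replace the 2-day minimum before each CV301 dose with an upper limit that the sponsor confirms.

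The cost is a protocol amendment with IRB review, a few later reports, and outcome follow-up for each reported pregnancy, including consent from partners.

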5.1.5 Maintenance Therapy

Maintenance therapy should start 4 weeks after completion of adjuvant therapy.

- Patients in the control arm (Arm A) will receive nivolumab alone on Day 1 of every 4 week cycle for up to 24 cycles (Cycles 13-36).
- Patients in the experimental arm (Arm B) will receive nivolumab on Day 1 of every 4 week cycle for up to 24 cycles (Cycles 13-36) and FVP-CV301 will be given concomitant every twelve weeks (every 3 cycles) for 8 doses.

Post-therapy patients will be under surveillance per NCCN guidelines with repeat CEA every 3 months for 2 years followed by every 6 months for 1 year (total 3 years), repeat CT of the C/A/P every 3 months for 2 years followed by every 6 months for up to 1 year (total 3 years), and colonoscopy at one year with repetition based on findings at the time of the procedure.

In the event of recurrence, the patient's disease and next line of therapy will be managed according to the individual cancer center's disease group management team. If the recurrence is within two years, the patient will continue to receive their scheduled nivolumab ± vaccine. In the event that administration of nivolumab ± vaccine is impacting the delivery or tolerability of standard of care next line therapy, patients will be removed from protocol therapy but will continue to be followed on study.

5.2 mFOLFOX6

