7. STUDY CALENDAR & EVALUATIONS

1 cycle = 14 days during neoadjuvant and adjuvant treatment 1 cycle = 28 days during maintenance treatment A = Arm A and B = Arm B	Screen	Arm B ± 2 days		Neoadjuvant Therapy C1- C4	Pre-Surgery	Surgery or Biopsy	Adjuvant Therapy C5-C12 ⁷	Maintenance C13-36 ¹¹	Safety Visits D30/D100 ¹²	Follow up ¹³
	D-28	D-28	D-14	± 2 days			± 2 days	D1 ± 2 days	+7 days	± 14 days
REQUIRED ASSESSMENTS										
Informed Consent	X									
Medical History including smoking history ¹	X									
Physical Exam ²	X	B	B	X	X		X ²	X	D30	X
Vital signs ECOG Performance Status ²	X	B	B	X	X		X	X	D30	X
ECG	X				X		C5D1			
AEs & concomitant medications	X	B	B	X	X		X	X	X	X
LABORATORY ASSESSMENTS										
Complete Blood Cell Count with diff (CBC)	X	B	B	X	X		X	X	D30	
Comprehensive Metabolic Profile (CMP)	X	B	B	X	X		X	X	D30	
CEA and CA19-9 ³	X				X		C8D1	X ¹¹		X ¹²
PT/INR and aPTT ⁴	X				X					
Thyroid Function ⁴	X	B		X	X		X ⁴	X ⁴		
Amylase & Lipase ⁴	X	B	B	X			X ⁴	X ⁴		
Pregnancy test (serum or urine) (WOCBP) ⁵	X ⁵	B	B	X ⁵			X ⁵	X ⁵		
DISEASE ASSESSMENT										
CXR ¹⁰					X					
CT or PET of chest ⁶	X				X ⁶		X ⁶	X ⁶		X ⁶
CT or MRI of abdomen and pelvis ⁶	X				X ⁶		X ⁶	X ⁶		X ⁶
TREATMENT EXPOSURE⁷										
mFOLFOX6				X			X			
Nivolumab		B	B	X			X	X		
Vaccination (Arm B ONLY)		B	B	X			X	X		
SPECIMEN COLLECTION										
Tumor Biopsy ⁸	X					X ⁸				
Blood sample for genomic DNA ⁹		B		A						
Blood Samples for correlative research ⁹		B		A	X		X ⁹			
FOLLOW-UP										
Survival Status, Subsequent Therapy										X

CBC with differential to include Hgb, Hct, RBC, WBC, ANC, platelet, MCV and CMP to include sodium, potassium, chloride, creatinine, blood urea nitrogen; liver function tests (LFTs) to include AST, ALT, total bilirubin (direct bilirubin if total is elevated), alkaline phosphatase

Key to Footnotes

1: Medical History. In addition, the following data will be obtained: smoking history questionnaire and a question about how the subject heard about the study. Prior treatment for colon cancer or other malignancies should be noted. If previously treated for colon cancer information regarding diagnosis, staging, treatment, and response should be obtained. Results of prior genomic testing will be requested and are required if available.

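### AE recording, SAE reporting and follow-up end when a new anti-cancer treatment starts, even for patients still receiving nivolumab with or without CV301

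*Combined protocol and SAP*

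**What the plan says.** Four bullets set the safety reporting rules. The first bullet of section 11.2.1 (AEs) and the first bullet of section 11.2.2.1 (SAEs) both run from signed consent "until 100 days after discontinuation of study drug(s) or until a new anti-cancer treatment starts, whichever occurs first". The last bullet of each section governs follow-up. For AEs related to study drug, follow-up ends on resolution, or when "deemed clinically insignificant, and/or until a new anti-cancer treatment starts, whichever occurs first". For all SAEs, related or not, the corresponding words are "and/or deemed clinically insignificant and/or until a new anti-cancer treatment starts, whichever occurs first".

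Section 5.1.5 deals with recurrence. The centre chooses the next line of therapy, and "If the recurrence is within two years, the patient will continue to receive their scheduled nivolumab ± vaccine". The patient leaves protocol therapy if study drug is found to be "impacting the delivery or tolerability of standard of care next line therapy". Section 5.1.3 has a parallel arrangement for patients found unresectable: the local team manages them, nivolumab (with the vaccine in Arm B) continues, and removal follows only if it interferes with standard care.

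Section 5.7.2 lists additional anticancer agents among the treatments excluded while study drug is being given. Radiation is also on that list, with a case-by-case exception for a symptomatic solitary lesion or the brain. Surgery and ablation are not on the list.

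**The concern.** The usual reason for closing a safety window at a new anti-cancer treatment is that the patient has left study drug and later events are hard to attribute to it. That reason fails if study drug continues. Here the trigger operates on its own: nothing in the four bullets requires study drug to have stopped, and the first of the two dates to occur decides.

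At stake is the reporting of SAEs in patients who receive an anti-PD-1 antibody, and in Arm B an investigational vaccine, together with another anticancer regimen. Under section 11.2.2.2, HCRN notifies the two suppliers on receipt of the site's SAE form. Under section 11.3, receipt of the same form prompts the summary on which the sponsor-investigator judges expectedness and relatedness. If the site is not obliged to submit the form, neither step is set in motion.

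**Working it through.** The plan states no figure on this point, so the check sets the passages side by side, with one piece of schedule arithmetic.

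**1. Does the trigger depend on study drug having stopped?** No. In the first bullets, the 100-day limb refers to discontinuation and the new-treatment limb does not; they are alternatives. In the last bullets, the new-treatment limb again stands alone.

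**2. Does the protocol foresee study drug together with next-line therapy?** Yes. Section 5.1.5 continues study drug after recurrence and removes the patient only if it affects next-line treatment. That condition makes sense only if both can be given together. Recurrence is not itself among the reasons for stopping protocol therapy in section 6.4.

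**3. Are doses still scheduled when such recurrences happen?** Inputs: adjuvant therapy starts about 6–8 weeks after surgery and has eight two-week cycles (5.1.4); maintenance starts 4 weeks after adjuvant therapy and has up to 24 four-week cycles (5.1.5).
- Cycle 12 Day 1: 6 + 7 × 2 = week 20, to 8 + 7 × 2 = week 22 after surgery.
- Cycle 13 Day 1: 20 + 4 = week 24 (4 weeks counted from Cycle 12 Day 1), to 22 + 2 + 4 = week 28 (counted from the end of Cycle 12).
- Cycle 36 Day 1: 24 + 23 × 4 = week 116, to 28 + 23 × 4 = week 120.

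Two years is 104 weeks. If it is counted from surgery, every recurrence within the limit falls at least 116 − 104 = 12 weeks before the last scheduled nivolumab dose. Section 5.1.5 does not give the starting point. Counted from the start of maintenance, the two-year limit falls 104 − 92 = 12 weeks after the last scheduled dose, so the latest recurrences would find no doses left. On either count, most of the two-year period has doses still to come.

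**4. Does section 5.7.2 remove the overlap?** Only in part. If it governs, concurrent systemic therapy largely disappears, but it then contradicts section 5.1.5. Even so, re-resection or ablation of a recurrence (a secondary objective in section 2.2) and permitted radiation could occur during dosing. Because the term new anti-cancer treatment is not defined, either could be read as closing the window.

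**5. Can the number affected be calculated?** No. It needs the share of patients who recur or are unresectable, start a treatment that counts as new, and stay on study drug. The documents give none of these for this trial.

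**The case against.** The strongest reply is that section 11.2 is coherent under section 5.7.2: if no other anticancer agent may be given during study drug, a new treatment implies that study drug has ended. Other text leans the same way. Section 6.4 stops protocol therapy when the investigator judges a change of therapy to be in the patient's interest. Calendar footnote 12 gives progression as one reason for permanently stopping study treatment. The calendar collects subsequent therapy only in the follow-up column. On this view the real conflict is between sections 5.1.5 and 5.7.2, and the reporting gap follows from it. This stands as a limit on the size of the problem. It does not remove the problem, because section 5.1.5 addresses recurrence specifically and provides for concurrent treatment.

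Several stronger readings are tempting but not supported:

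- **Direct contradiction with section 6 and the calendar.** Section 6 says "Subjects will be evaluated for adverse events (all grades), serious adverse events, and adverse events requiring study drug interruption or discontinuation", and the calendar has a row for "AEs & concomitant medications". These govern assessment at visits, not the period for recording or submitting events. Footnote 13 schedules AE assessments well beyond 100 days, so the two periods already differ by design.
- **A count of affected patients.** A reader might convert the median RFS values in the Figure 1 legend into expected recurrences among the 70 resected patients. That would count recurrences, not overlap, and would borrow from a non-randomised comparison. It would also leave out unresectable patients (74 − 70 = 4 to 78 − 70 = 8 under section 12.3), so it is not even an upper bound.
- **A gap during protocol chemotherapy.** One might fear that the 100 days could lapse while mFOLFOX6 continues after nivolumab has stopped. Section 6 treats it as one of the study drugs: "The investigator may attribute each toxicity event to the vaccine, nivolumab, mFOLFOX6, or any component of the combination therapy". On that reading the 100 days have not begun.
- **A defect in footnote 12.** Its new-treatment stop applies to events ongoing at the D30 visit, after study treatment has permanently ended, so it is consistent.
- **Loss of data to the DSMC.** Sections 13.1 and 13.2 describe summary reports from HCRN, but nothing says that these start from the SAE form.

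**Conclusion.** The gap is real. As written, sections 11.2.1 and 11.2.2.1 allow a site to stop recording AEs, reporting SAEs and following events in a patient who is still being dosed, and section 5.1.5 describes patients in that position. Section 5.1.3 may add unresectable patients, depending on what the local team gives them.

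The extent is conditional on how sections 5.1.3, 5.1.5 and 5.7.2 are reconciled and on how many patients stop study drug at progression. It cannot be quantified from the documents, and no bound should be quoted. The conclusion rests on a literal reading of the four bullets; some sites may in practice keep reporting. The primary endpoint and survival follow-up are not affected. This is a safety-reporting matter that should be corrected, not a threat to the efficacy analysis.

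**What to change.** In the first and last bullets of sections 11.2.1 and 11.2.2.1:

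1. State that a new anti-cancer treatment does not end recording, reporting or follow-up while any study drug is being given, and that the trigger applies only after the last dose of the last study drug.
2. State whether re-resection, ablation or palliative radiation counts as a new anti-cancer treatment for reporting purposes.
3. Have the sponsor say how the 100-day window applies to a patient already on next-line therapy when study drug stops: whether it runs in full or closes at the last dose.

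Separately, sections 5.1.3, 5.1.5 and 5.7.2 must be reconciled on concurrent anticancer therapy. No view is taken here on which clinical rule should govern. The reporting change is worth making whichever way that is settled, since local treatment of a recurrence could still fall within dosing.

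The cost is wording in four bullets, one definition and the reconciliation. Sites would enter somewhat more AE and SAE data, mostly at visits where calendar footnote 11 already requires an AE assessment before each maintenance treatment.
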